3 OBJECTIVES AND ENDPOINTS

OBJECTIVES	ENDPOINTS	JUSTIFICATION FOR ENDPOINTS			
Primary					
To determine whether treatment of high grade DFU with standard care plus TTAX01 results in a higher probability of achieving complete wound closure over 26 weeks, compared with standard care alone.	Time from baseline to initial observation of healing, over 26 weeks, where healing has been confirmed at two consecutive visits each two weeks apart.	The endpoint complies with FDA guidance. Dropouts should be minimal during the first 26 weeks, but may increase thereafter. Analysis will use a Cox proportional hazard model			
Secondary					
To compare differences between treatment groups in proportions of wounds healed through 50 weeks	Proportions of wounds healed by Week 50	This endpoint provides insight into longer term benefits of the intervention			
To compare long term durability of closure between treatment groups	Proportions of wounds that re-ulcerate by Week 50	May provide insight into the quality of healing			
To compare limb preservation between treatment groups	Proportions of minor (portions of the foot) and major (ankle, above or below the knee) amputations following the initial procedure by Week 50	Each amputation risks loss of mobility, with consequent increased mortality			
To compare patient reported mobility (lower extremity function) between groups.	Total score on PROMIS Health Organization Neuro- QoL "Lower Extremity Function" at Study End.	The tool is an NIH validated measure of patient reported outcomes			
Safety					
To examine Quality of Life endpoints related to therapeutic intervention	Total score of quality of life assessment determined by Cardiff Wound Impact Schedule (CWIS) at Study End				
Proportion of subjects experiencing adverse events, by group	Spontaneously reported and elicited adverse events, coded in MedDRA				

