8.1.11 Early Termination Visit

If a subject is withdrawn from their randomized treatment for any reason, they should be encouraged to continue with the subsequent scheduled visits for observation. The Observational Period visits are particularly valuable in monitoring long-term adverse events, (e.g., unresolved ongoing adverse events, and new treatment related adverse events including limb amputation for ulcers that do not heal).

If a subject is being withdrawn from the trial, attempt to schedule an early termination visit at which the End of Study procedures are carried out (refer to Section 8.1.6). Complete procedures described therein and document the reason for the subject's withdrawal.

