9.4.3 Analysis of the Secondary Endpoints

Secondary efficacy endpoints in this study include proportions of index ulcer healed by Week 50, proportions of wound re-ulcerations by Week 50, proportions of minor and major amputations by Week 50, and total score of PROMIS Lower Extremity Function Questionnaire at end of study.

The non-parametric Cochran-Mantel-Haenszel (CMH) test with adjustment for baseline wound size cohort will be used to examine treatment effects for the SC plus TTAX01 arm vs. SC alone arm on proportion of subjects with index ulcer achieving and remaining healed at Week 50, proportion of subjects (among those with complete wound healing before Week 50) with wound re-ulceration at Week 50, and proportion of subjects with minor and/or major amputations by Week 50. Subjects' missing values at Week 50 in these endpoints, due to either no assessment or early termination from the study, will be imputed using the last-observation carry forward (LOCF).

An analysis of covariance model (ANCOVA) with treatment and baseline wound size as effect will be used to analyze total score of PROMIS Lower Extremity Function Questionnaire at end of study. Subjects' missing values in this endpoint, due to either no assessment or early termination from the study, will utilize the assessment collected at the early termination visit.

The analyses of the secondary efficacy endpoints will be performed for the ITT population and PP population as well as the LO population.

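### LOCF at Week 50 scores leavers who were event-free at their last visit as free of amputation or re-ulceration to Week 50; the healing and PROMIS rules are also incomplete

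*Protocol*

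**What the plan says.** Section 9.4.3 names three binary secondary endpoints:

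- healing: "proportion of subjects with index ulcer achieving and remaining healed at Week 50";
- re-ulceration: "proportion of subjects (among those with complete wound healing before Week 50) with wound re-ulceration at Week 50";
- amputation: "proportion of subjects with minor and/or major amputations by Week 50".

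On the test it says: "The non-parametric Cochran-Mantel-Haenszel (CMH) test with adjustment for baseline wound size cohort will be used". Missing Week 50 values, "due to either no assessment or early termination from the study, will be imputed using the last-observation carry forward (LOCF").

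For the PROMIS score the same section covers the same two causes of missingness (no assessment, early termination) and says that such subjects "will utilize the assessment collected at the early termination visit". The Schedule of Activities (1.3) has PROMIS at Screening and at Visit 29 only.

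On dropout, section 3 says: "Dropouts should be minimal during the first 26 weeks, but may increase thereafter". Section 8.1.11 describes an early termination visit "at which the End of Study procedures are carried out (refer to Section 8.1.6"). Section 8.1.6 is the Bi-Weekly Observation Period; the End of Study Visit is 8.1.8.

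**The concern.** Amputation and re-ulceration accumulate over follow-up. Carrying forward an event-free status assigns zero risk to every week after the subject was last seen. Follow-up time therefore affects the endpoint: the shorter an arm is observed, the fewer events it can show. Section 3 expects dropout to rise after Week 26, which is about half of the 50-week window. The trial is open label (6.3), so unequal dropout is plausible. For the primary endpoint, section 9.4.2 censors leavers and so avoids this assumption. Section 9.4.3 brings it in for the later endpoints, where more dropout is expected.

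At stake is the limb-preservation comparison, which section 3 justifies by loss of mobility and mortality. Reported rates would be too low in both arms, and the between-arm difference could partly reflect who stayed. Two further gaps concern what is imputed: which healing status is carried forward, and which PROMIS value applies when there was no early termination visit.

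**Working it through.** **Inputs.** The protocol gives no Week 50 amputation or re-ulceration risk and no dropout by arm. Its only dropout figure is the 10% used for sample size (9.2). The risks and dropout splits below are therefore assumptions, with the same true risk in both arms.

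**Step 1: exponential event and dropout times.** Let p be the true 50-week risk and d the dropout proportion, with a = −ln(1−p) and b = −ln(1−d). LOCF counts an event only if it comes before exit, so the expected LOCF rate is

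a/(a+b) × [1 − (1−p)(1−d)].

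For p = 20%, a = 0.2231.

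| Dropout | b | a/(a+b) | 1 − (1−p)(1−d) | LOCF rate |
|---|---|---|---|---|
| 10% | 0.1054 | 0.679 | 0.28 | 19.0% |
| 20% | 0.2231 | 0.500 | 0.36 | 18.0% |
| 30% | 0.3567 | 0.385 | 0.44 | 16.9% |

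With 10% v 30% dropout the false difference is 19.02 − 16.93 = 2.1 points, in favour of the arm with more dropout. With equal dropout both arms read the same, so the false difference is zero.

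**Step 2: a different exit pattern.** If exits are uniform over 50 weeks, a leaver's chance of having had the event already is 1 − p/a = 1 − 0.2/0.2231 = 10.4%. The LOCF rate is (1−d)p + d × 0.104:

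- 10% dropout: 0.9 × 0.2 + 0.1 × 0.104 = 19.0%;
- 30% dropout: 0.7 × 0.2 + 0.3 × 0.104 = 17.1%.

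The difference is 1.9 points. With 125 per arm the standard error is √(2 × 0.181 × 0.819/125) = 0.0487, so the shift is about 0.4 standard errors. An unstratified two-sided 5% test then rejects 6.8% of the time under no true difference. For true risks of 10% and 30% the shift is 1.0 and 2.8 points, with rejection of 5.8% and 7.9%.

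**Step 3: a low-risk case.** In Phase 2 (2.2), two of 32 subjects needed minor amputations within 16 weeks, or 6.25%. With p = 6.25% in the Step 1 formula, 10% v 30% dropout gives 5.9% v 5.3%, a shift of 0.7 points before rounding.

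**Step 4: dropout and amputation sharing a risk factor.** Take a mean-one lognormal frailty (log-scale SD 1.0) that multiplies both hazards, with base rates of 20% (event) and 30% (dropout). The true risk becomes 17.6% and realised dropout about 25%. LOCF reads 13.6%. Kaplan-Meier with leavers censored reads 15.5%. Censoring thus recovers 1.9 of the 4.0 points lost.

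**Step 5: healing.** If the endpoint were first healing and leavers kept their last status, the direction reverses. With uniform exits and 10% v 30% dropout, a true 42.5% reads 40.6% v 36.7% (3.9 points) and a true 65% reads 62.3% v 56.9% (5.4 points), so the arm with more dropout looks worse. The endpoint, however, also requires the wound to stay healed. A healed leaver is carried forward as still healed, which pushes the other way.

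**Step 6: which healing status.** Section 8.2 requires two additional observations at two-week intervals. Section 9.4.2 censors subjects without confirmation data for the primary endpoint. Section 9.4.3 has no equivalent sentence for Week 50.

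**Step 7: PROMIS.** Section 9.4.3 names two causes of missingness but gives one substitute, the early termination value. A subject who reaches Visit 29 and does not complete the questionnaire has no early termination visit, and the only other scheduled PROMIS is at Screening. The rule gives no value for a case that it names.

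**The case against.** Several points on the other side stand.

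- These are secondary endpoints, and section 9.4.1 leaves sensitivity analyses and missing-data detail to the SAP, which is not at hand. LOCF is nevertheless a rule that the protocol states, so the objection is to a choice made and not to missing detail.
- The size rests on assumed figures. At the protocol's own 10% dropout in both arms there is no between-arm bias under no difference, and at a Phase 2-like risk the shift is 0.7 points.
- Censoring also assumes non-informative dropout, and Step 4 shows that it removes only about half the error when that fails.

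Three stronger readings are tempting, and the protocol does not support them.

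- A reader might infer that every early leaver is scored as never amputated and never re-ulcerated. LOCF keeps events recorded before exit, and section 7.2 lists limb amputation among the reasons for discontinuation. Scoring all leavers event-free would give 0.2 × 0.7 = 14.0% at 30% dropout, not 16.9%. Re-ulceration also concerns only subjects who had healed.
- A reader might infer that an unconfirmed closure at the last visit counts as healed. Section 9.4.3 does not say so, and 8.2 points the other way. The text is ambiguous.
- A reader might infer from the 8.1.6 reference that leavers give no PROMIS. The same sentence calls for End of Study procedures, sections 7.2 and 8.1.4 send leavers to that visit, and 8.1.8 lists PROMIS. The reference is a slip.

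**Conclusion.** The point holds in limited form. LOCF understates cumulative amputation and re-ulceration because it gives event-free leavers no further risk. With unequal dropout it favours the arm that loses more subjects on these two endpoints. The false difference is about 2 points for an assumed 20% risk with 10% v 30% dropout (1.9 or 2.1 depending on exit pattern), and between 0.7 and 2.8 points over the other risks tried. Two-sided rejection under no difference is 5.8% to 7.9% for risks of 10% to 30%. With equal, non-informative dropout and no true difference the between-arm bias is zero.

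For healing, the direction cannot be fixed in advance and the status carried forward is unclear. For PROMIS, the rule is incomplete for completers with a missing questionnaire. The matter should be corrected, but the primary analysis does not depend on it.

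**What to change.** In section 9.4.3:

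1. Analyse first amputation (from randomization) and first re-ulceration (from confirmed closure, among healed subjects) as time-to-event outcomes. Treat death as a competing event, compare arms within wound-size strata, and censor leavers at last contact. Keep CMH with LOCF as a sensitivity analysis.
2. State that only confirmed closure is carried forward as healed.
3. Give a PROMIS rule that covers completers with a missing questionnaire, for example multiple imputation using arm, screening PROMIS and wound size.

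In section 8.1.11, change the reference from 8.1.6 to 8.1.8.

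This needs text changes only. No visit or assessment is added: adverse event onset dates (8.4.4) and wound status by visit are already collected. The costs are slightly more analysis work and usually higher reported event rates. Censoring still assumes non-informative dropout, so bias is reduced but not removed when dropout and events share a risk factor.

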6.3 Measures to Minimize Bias – Randomization and Blinding

Subjects will be randomly assigned to one of two groups, by study, using a predetermined block size. Stratification based on wound size post debridement at baseline (post debridement

wound size <= 8.0 cm² vs. wound size > 8.0 cm²) will help to avoid spurious results driven by an imbalance in distribution of variables within this parameter which has a known correlation with probability of healing. Gender and wound duration are expected to distribute normally without the need for stratification. Bias will be further controlled by distributing enrollment over twenty or more clinical sites.

Due to the nature of the test article, the trial is open label, with no blinding of the site staff. The determination of wound closure will be made by the Investigator based on visual and tactile assessment of the wound. To reduce bias in the ascertainment of closure, one independent blinded reviewer will review the image obtained from a wound measurement device (eKare inSightTM) in each case where the Investigator makes a determination of closure. Discordant opinions will be adjudicated by a second independent blinded reviewer who will examine multiple additional images taken at various angles to the wound surface.

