- Specific gravity
- pH
- Protein
- Glucose
- Ketones
- Occult blood
- Leukocyte esterase
- Nitrite
- Bilirubin
- Urobilinogen.

Refer to the laboratory manual for the collection of bloods, storage, and shipping information.

^{*:} If protein, leukocyte, occult blood, or nitrites are positive, microscopic examination is performed.

 Administer the PROMIS Lower Extremity Function questionnaire and the CWIS (examples shown in the Appendix)

If the subject qualifies and can begin the initial procedure on the same day as screening, then proceed directly to the Initial Procedure (refer to Section 8.1.2). Otherwise,

- Apply wound dressing including a non-adherent, standard foam pad or alginate dressing (e.g., hydrogels, foam dressings, and alginates) that is appropriate for the amount of drainage, and a secondary bandage to ensure a moist ulcer environment, which adequately controls exudate and avoids maceration of the surrounding skin
- Empiric, systemic antibiotic therapy may be started at this time if clinically indicated, in advance of biopsy for culture at the initial procedure visit. Topical antibiotics should not be administered
- Schedule the Initial Procedure Visit (may be the same day as Screening Visit or within (7) seven days once all eligibility criteria have been confirmed)

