8.1.8 End of Study Visit (Visit 29; Day 344 ± 7)

[Purpose]: To document the patient status if they complete the entire treatment period or if they are withdrawn from the study during this period.

Begin with the following procedures:

- Assess adverse events
- Review any changes in concomitant medications
- Obtain photograph of the index ulcer using the electronic wound imaging and measuring device
- Assess the index ulcer

If at this visit a previously unhealed index ulcer is observed to be closed,

perform the following procedures:

- Assess adverse events
- Review concomitant medications
- Assess subject compliance regarding off-loading since the last visit
- Obtain photographs of the closed ulcer using the electronic wound imaging and measuring device

 Observe the wound – if it is fully epithelialized with no drainage or need for a dressing, record it as closed.

The next visit scheduled will serve as the first consecutive confirmation visit in 14 ± 2 days and will begin the confirmation of closure procedures (refer to Section 8.1.9).

Otherwise,

- Perform physical examination, including vital signs (i.e., heart and respiratory rates, blood pressure, and temperature while patient is seated)
- Perform Laboratory Assessments as listed in Table 8.1.1-1 including the pregnancy test for females of childbearing potential
- Instruct subject to complete the PROMIS Lower Extremity Function questionnaire and the CWIS.

Complete subject disposition forms and exit the subject from the study.

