For total score of CWIS and PROMIS Questionnaires, the null hypothesis is that a total score (or better quality-of-life) of this measure will not be statistically different between the two treatment arms of this study at the end of study. The alternative hypothesis is that a greater total score (or better quality-of-life) of one or both of these measures will be seen for the SC plus TTAX01 arm at the end of study, compared to the SC alone arm.

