9.4.5 Baseline Descriptive Statistics

The following subject demographic and baseline data will be collected and reported:

Demographic variables will include but not limited to the following:

- Age
- Gender
- Ethnicity
- Race
- Smoking status

- Medical history
- Disease diagnosis, index ulcer measurement, severity, and prior treatment
- Physical examinations
- Laboratory tests
- PROMIS and CWIS QoL measures

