12.3 Cardiff Wound Impact Schedule

The subject will be provided with,	and asked to complete the following:
------------------------------------	--------------------------------------

How ofter	n do you see your	family and friend	s?
Daily □	Once a week □	Once a month □	Less than once a month \Box
How stres	ssful has this expe	erience been for yo	ou during the past 7 days?
		N	Not at all/

	not an an/ not applicable	Slightly	Moderately	Quite a bit	Very
Difficulty getting out and about	5	□ 4	3	2	1
Relying more on others	□	□	□	□	□
	5	4	3	2	1
Your family/friends being overly protective	□ 5	□ 4	□ 3	□ 2	1
Unable to enjoy your usual social life (e.g. hobbies)	□ 5	□ 4	3	2	1
Limited contact with family/friends	□	□	□	□	□
	5	4	3	2	1
Not going out for fear of bumping your wound site	□	□	□	□	□
	5	4	3	2	1
Wanting to withdraw from people	□	□	□	□	□
	5	4	3	2	1

Have you experienced any of the following during the past 7 days?

	Not at all/ not applicable	Seldom	Sometimes	Frequently	Always
Difficulty getting out and about	□ 5	□ 4	□ 3	□ 2	□ 1
Relying more on others	□ 5	□ 4	□ 3	2	□ 1
Your family/friends being overly protective	5	□ 4	□ 3	2	1
Unable to enjoy your usual social life (e.g. hobbies)	5	4	3	2	1

Page	06	of 1	$\Omega\Omega$
Fage	ソロ	OII	1111

111111				1 484 7 0 01 1	
Limited contact with family/friends	□ 5	□ 4	□ 3	□ 2	□ 1
Not going out for fear of bumping your wound site	5	□ 4	□ 3	2	1
Wanting to withdraw from people	□ 5	□ 4	□ 3	□ 2	1

To what extent do you agree/disagree with the following statements?

	Strongly disagree	Disagree	Not Sure	Agree	Strongly Agree
I feel anxious about my wound(s)	5	□ 4	3	2	1
I feel frustrated with the time it is taking for the wound(s) to heal	5	□ 4	3	2	□ 1
I am confident that the wound(s) I have will heal	□	□	□	□	□
	5	4	3	2	1
I worry that I may get another wound in the future	□	□	□	□	□
	5	4	3	2	1
The appearance of the wound site is upsetting	□	□	□	□	□
	5	4	3	2	1
I worry about bumping the wound site	□	□	□	□	□
	5	4	3	2	1
I worry about the impact of the wound(s) on my family/friends	5	□ 4	□ 3	2	□ 1

Have you experienced any of the following during the past 7 days?

	Not at all/ not applicable	Seldom	Sometimes	Frequently	Always
Disturbed sleep	5	□ 4	3	□ 2	□ 1
Difficulty in bathing	5	4	3	2	1

Page 97 of 100

Immobility around the home	□	□	□	□	□
	5	4	3	2	1
Immobility outside the home	□	□	□	□	□
	5	4	3	2	1
Leakage from the wound(s)	□	□	□	□	□
	5	4	3	2	1
Pain from the wound site	□	□	□	□	□
	5	4	3	2	1

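### The PROMIS analysis of covariance leaves out the screening PROMIS score, which gives up precision and leaves a chance imbalance in baseline mobility uncorrected

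*Protocol*

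**What the plan says.** **Model.** Protocol Section 9.4.3 names the effects in full: "An analysis of covariance model (ANCOVA) with treatment and baseline wound size as effect will be used". The outcome is the final score, not a change: the model is to "analyze total score of PROMIS Lower Extremity Function Questionnaire at end of study". A subject without an end-of-study value contributes the one from the early termination visit.

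**Data available.** Section 8.1.1 has the sites "Administer the PROMIS Lower Extremity Function questionnaire and the CWIS" at screening. Section 8.1.8 repeats this at Visit 29: "Instruct subject to complete the PROMIS Lower Extremity Function questionnaire and the CWIS". The Schedule of Activities (Section 1.3) marks the same two time points. Section 9.4.5 lists "PROMIS and CWIS QoL measures" among the baseline data to be reported.

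**Balance.** Section 6.3 provides for one factor only: "Stratification based on wound size post debridement at baseline".

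**Hypotheses.** Section 9.1 treats PROMIS and CWIS together. Its alternative is that "a greater total score (or better quality-of-life) of one or both of these measures will be seen for the SC plus TTAX01 arm". Section 3 puts CWIS under safety, the lists of secondary endpoints in Sections 9.1 and 9.4.3 leave it out, and Section 9.4.4 gives its total score among the safety tables.

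**The concern.** A subject's earlier score on the same 19-item questionnaire is a natural candidate to explain variation in the later one. The protocol collects it before allocation, tabulates it, and omits it from the one model where it would help. The primary Cox model in Section 9.4.2 does adjust for baseline ulcer size and duration because of their possible effect on the outcome, so the principle is already accepted.

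Patient-reported mobility is a named secondary objective, and two things are at stake. The confidence interval for the treatment difference is wider than these data require. If the arms also happen to differ in starting mobility, the stated model cannot remove that difference, because neither the stratification nor the covariates refer to mobility.

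Separately, a reader of Section 9.1 would take CWIS to be tested alongside PROMIS, with a favourable result on either one sufficient. A reader of Sections 3 and 9.4.4 would not.

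**Working it through.** **Inputs.** From the protocol: 250 subjects (synopsis) randomized 1:1 (Section 9.2), so 125 per arm, and two-sided tests at 5% (Section 9.4.1). There is no planned PROMIS figure to reproduce: Section 9.2 sizes only the primary endpoint, and no effect size, standard deviation, correlation or power is given for PROMIS. The partial correlation ρ between screening and final PROMIS, given wound size, is therefore an assumption. It is varied from 0.2 to 0.7.

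**Precision.** Adding a baseline with partial correlation ρ multiplies the residual variance by 1 − ρ². The standard error is multiplied by √(1 − ρ²), and the gain is equivalent to multiplying the sample size by 1/(1 − ρ²). These ratios do not depend on the sample size.

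| Assumed ρ | √(1 − ρ²) | Cut in standard error | 1/(1 − ρ²) | Equivalent extra subjects |
|---|---|---|---|---|
| 0.2 | 0.980 | 2% | 1.04 | 4% |
| 0.3 | 0.954 | 5% | 1.10 | 10% |
| 0.5 | 0.866 | 13% | 1.33 | 33% |
| 0.7 | 0.714 | 29% | 1.96 | 96% |

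**Power.** With 125 per arm and every subject contributing, the standard error in units of the residual SD is √(2/125) = 0.1265. The difference detectable with 80% power under the stated model is (1.960 + 0.842) × 0.1265 = 0.354 SD. With the screening score added, the detectable difference is 0.354 × √(1 − ρ²). This gives 0.347, 0.338, 0.307 and 0.253 SD for ρ = 0.2, 0.3, 0.5 and 0.7. An effect of 0.354 SD would then have power of 81.6%, 83.6%, 89.9% and 97.5%.

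**Chance imbalance.** Suppose the arms differ at screening by 1.96 standard errors, which is 1.96 × 0.1265 = 0.248 SD. The stated model's estimate then shifts by ρ × 0.248: 0.074 SD at ρ = 0.3, 0.124 SD at 0.5 and 0.174 SD at 0.7. Given that imbalance, and with no treatment effect, the test statistic is normal with mean 1.96ρ and variance 1 − ρ². The chance that it passes ±1.96 is about 7.9%, 12.9% and 20.5% for those three values. An imbalance of only 1 standard error does not raise this chance above 5% (5.0%, 4.8% and 3.9%), although the estimate still shifts, by 0.038, 0.063 and 0.089 SD.

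**Either-or hypothesis.** The alternative in Section 9.1 points in one direction, towards TTAX01. With a two-sided 5% test, a false result in that direction has a chance of 2.5% per measure. For at least one of two measures:

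- independent test statistics: 1 − 0.975² = 4.9%
- correlation 0.7 (assumed), from the bivariate normal distribution: 4.2%

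**The case against.** **Validity.** It can fairly be said that the omission is an efficiency choice and not an error of inference. That stands. Under randomization the stated model is unbiased and its type I error is 5%. A reader might infer that a baseline difference will pass as a treatment effect or inflate the error rate. The documents do not support that in general: the raised rates above hold only given a large imbalance that has actually occurred, and the 5% level already averages over such occurrences. Baseline PROMIS is also reported, so an imbalance would be seen, though seeing it does not correct the estimate.

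**Size.** The gain rests on a correlation that the protocol does not give. Screening comes before an operation that may include bone resection or minor amputation, and the final score comes some 50 weeks later. Both may lower ρ, and at 0.2 to 0.3 the standard error falls by only 2% to 5%. This is why the range starts at 0.2. The endpoint is also one of several secondaries and is not separately powered.

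**Left to the SAP.** Section 9.4.1 defers detailed methods to the SAP. That does not answer the point, because Section 9.4.3 already names the model's effects and an SAP that added one would depart from it.

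**CWIS error rate.** A reader might compute the either-or error as about 8.4% to 9.8%, by counting any significant difference on either measure. That includes results favouring control, which the directional alternative does not count. Section 9.1 also states hypotheses and does not label them a success rule. The general sentence in Section 9.4.1 about superiority comparisons for all data leaves the role of CWIS unclear. It does not remove the conflict.

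**CWIS scoring.** A reader might infer from the printed codes that the item "I am confident that the wound(s) I have will heal" is counted backwards, since strong disagreement carries the code 5. The protocol nowhere says that the CWIS total is a raw sum of those codes, and the question on seeing family and friends has no code at all. The appendix is not a scoring algorithm, so this inference is not supported.

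**Conclusion.** The point holds as a precision improvement to a valid analysis. Section 9.4.3 fixes a PROMIS model without the screening score, although that score is available before randomization. For an assumed partial correlation of 0.2 to 0.7, the cost is a standard error that could have been about 2% to 29% smaller. The true value could lie anywhere in that range or outside it. Protection against an observed imbalance in starting mobility is a further reason to adjust, but it is not evidence that the planned test is wrong.

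The conflict over CWIS between Section 9.1 and Sections 3 and 9.4.4 is real and secondary. Read as two tests, it raises the chance of a false favourable finding from 2.5% to about 4.2% to 4.9%, for test correlations from 0.7 down to 0. Neither point touches the primary endpoint.

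**What to change.** In Section 9.4.3, add the screening PROMIS total as a continuous covariate, so that the model is treatment + baseline PROMIS + baseline wound size. In Section 9.1, make PROMIS the only tested patient-reported endpoint and leave CWIS descriptive, in line with Sections 3 and 9.4.4.

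The cost is one model term and an edit to one paragraph. No new data, visits or subjects are needed. The change should be made before outcome data are seen, since a covariate added later would look chosen from the results.
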